A.3.1. Experiment. We will enroll the patients from Aim 2 all of whom completed the community-based exercise intervention and underwent pre/post neuroimaging protocols. • Neuropsychological examination. Subjects will undergo follow-up neuropsychological examination to quantify neurocognitive functioning and neuropsychiatric symptomatology. The neuropsychological examination protocol will be the same outlined in A.1.1.1.

A.3.2. Analysis and statistical plan. Our main exploratory hypothesis is that the degree of improvement in glymphatic functioning (per DTI-ALPS) and decreased beta-amyloid burden (per PET) will significantly associate with neurobehavioral dysfunction improvements. We will also explore whether scalar degree of treatment compliance relates to degree of change in our assessment modalities. Statistical analysis will be overseen by statistics Co-I [name] and the same considerations outlined in Aims (1) will be applied. To test Hypothesis (3A) a paired Student's t-test or Wilcoxon signed-rank test, depending on normality findings, will be applied to determine if memory and executive functioning domain averages are improved after, relative to before, exercise intervention. We have powered this aim based on recent literature that has shown a medium improvement in executive functioning in between subject design (spatial working memory task, np2 = 0.17; MoCA global cognitive screen, np2 = 0.133; Treatment n = 24, Control n = 9) and large effect size withinsubject design (TMT-B-A time, np2's = 0.34; n = 19)70. To test Exploratory Hypothesis (3B), a paired Student's t-test or Wilcoxon signed-rank test, depending on normality findings, will be applied to determine if PROMIS – SRI and SD symptom scores are reduced is after, relative to before, exercise intervention. To test Exploratory Hypothesis (3C), two multivariate linear regressions will be employed, both will enter mean memory and

mean executive functioning domain scores as independent variables, with one regression using DTI-ALPS score and the other using cortical:cerebellar SUVr ratio as sole dependent variables. Exploratory Hypothesis (3D) analysis will be the same, with PROMIS – SRI and SD symptom scores substituted as independent variables. *A.3.3. Impact.* Results will provide evidence of how CNS lymphatic and beta-amyloid burden response to regular vigorous exercise in a PD sample relates to neurobehavioral functioning, as a clinical outcome metric.

B. Limitations and alternative strategies. BOLD CVR-weighted maps are derived from susceptibility induced changes around capillaries and veins, but periarterial spaces are also relevant. While the BOLD contrast directly originates around capillary and post-capillary vasculature, venules and veins are central to perivascular fluid clearance. Furthermore, the changes are dependent on compliance of the arteriolar microvasculature, as dHb in veins will not occur without arteriolar vasodilation. Thus, dysregulation of both vessel types will manifest in the observable, and we provide preliminary data on the relevance of these measures and their relationship to choroid plexus activity. Methods are too complex and will not be generalizable. A major focus of our work is to provide tools that are generalizable and can be implemented on different scanner platforms by non-specialists, and contrast evaluated using graphical software. We have also recently implemented our lymphangiography procedure on the clinical scanners at Vanderbilt Children's Hospital for evaluation of perioperative cardiac surgeries (e.g., chylothorax). The diffusivity measure could be due to blood flow. At the chosen b=1000 s/mm2, spins within fast flowing venous blood should be completely suppressed. Aim 1 focuses primarily on intracranial glymphatic flow; how will the other data be included? The imaging protocol includes multiple measurements of the CNS lymphatic system. To reduce concerns with multiple comparisons, Aim 1 has been powered based on our most promising preliminary data (DTI-ALPS score, obtained in 61 older subjects with and without aMCI). If Aim (1) findings suggest that other CNS lymphatic system measures are more promising, we will use these measures in Aims (2-3) as well to investigate their dependency on betaamyloid burden.

Patient heterogeneity is a concern. Since other clinical factors can affect brain and cognitive functioning, we plan to control for age and screen for the most common medical conditions that might disproportionally affect outcome assessments. Furthermore, we have selected an age-cutoff that reduces clinical heterogeneity and has extant support for the presence of our conditions-of-interest. Patient recruitment. Vanderbilt University Medical Center's Neurology division has a large clinical volume of adult patients with Parkinson's. Thus, our recruitment target is felt to be reasonable. Patient attrition. We have accounted for a possible 10% attrition/exclusion in our protocol. We will use compliance as a scalar variable, allowing us to retain all patients at follow up, regardless of degree of compliance.

C. Sex as a biological variable. Given the relative infancy of the field of human CNS lymphatic imaging, to our knowledge there is no literature reporting sex differences for all proposed biomarkers of the lymphatic drainage system. Therefore, we have powered our study to specifically address this concern, and subjects will be recruited equally for both sexes and statistical measures are in place to evaluate how each observable varies with biological sex. This should be the first study to report how these properties of the lymphatic system differ with biological sex in humans.

D. Scientific rigor and reproducibility. The need to understand CNS small blood and lymphatic vessels is becoming increasingly recognized, with more than 150 manuscripts published in the last five years on this topic. However, nearly all studies utilize animal models only, and there is much less information available on how this system operates in humans in health or in the presence of clearance disorders such as Alzheimer's disease. One reason for this is that reliable methods for evaluating lymphatics in vivo are underdeveloped. Methods proposed here (e.g., CVR compliance, lymphangiography, glymphatic flow, and CSF flow velocity)

have already been evaluated by us for reproducibility, and lymphatic methods have been optimized in prior work in patients with lymphatic insufficiency of known etiology (e.g., A.1.3.). Finally, each aim includes a statistical analysis section in which power calculations are provided based on our preliminary data and available extant literature. The statistical analysis of all aims will be overseen by biostatistician collaborator [name] to ensure responsible analysis and interpretation of the results.

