2 STUDY DESIGN

2.1 OVERALL DESIGN

For the PD cohort, participants will be recruited from Vanderbilt University Medical Center Neurology's Behavioral and Cognitive and Movement Disorder Clinics by Drs. [name] and [name]. We will prospectively enroll participants with idiopathic Parkinson's disease (n=50; age range=55-80 years), equally distributed and matched for age and sex between groups with (n=25) and without (n=25) mild

cognitive impairment. These populations provide a cohort to evaluate the potential relationship between glymphatic flow and beta-amyloid burden, given the elevated risk of beta-amyloid accumulation associated with PD and MCI conditions. Patients will have medical and motor presentation indicated for the community-based exercise program. Those patients with clinically-defined MCI, will be without evidence of vascular cognitive impairment, primary mood disorder, or comorbid medical condition that could contribute to cognitive symptoms (e.g. pulmonary, hematologic, metabolic, or vitamin deficiency). Potential participants will undergo a neurological and neuropsychological examination (including cognitive exam and behavioral/symptom questionnaires) to characterize their medical and neurobehavioral status. They will then undergo baseline neuroimaging protocols, both MRI brain scan (DTI-ALPS) and PET/CT (C11PiB) brain scan. Actigraph will be attached to the patient to continuously monitor motor activity. A background monitor of typing cadence will be activated on their computer to monitor for changes in fine motor control. The cohort will complete the same clinical and neuroimaging assessments after they participate in a 12-week community-based exercise intervention. Specifics about assessments and the exercise program are as follows.

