1 STATISTICAL PLAN

1.1 AIM 1

Aim (1). To quantify the relationship between CNS lymphatic measures and beta-amyloid burden.

- Hypothesis (1A). Glymphatic flow and lymphatic collector velocity inversely correlate with beta amyloid measured from 18F-florbetapir PET in older adults with Parkinson's disease.
- Exploratory Hypothesis (1B). In Parkinson's subjects matched for age and sex, glymphatic flow and betaamyloid burden will be worse in patients with versus without mild cognitive impairment (MCI).

A.1.1 Experiment. We will enroll participants with idiopathic Parkinson's disease (n=32; age range=55- 80 years), equally distributed and matched for age and sex between groups with (n=16) and without (n=16) mild cognitive impairment. These populations provide a cohort to evaluate the potential relationship between glymphatic flow and beta-amyloid burden, given the elevated risk of beta-amyloid accumulation associated with both conditions. These patients will form a cohort to be assessed before and after a community-based exercise intervention. Participants will be recruited from Vanderbilt University Medical Center Neurology's Behavioral and Cognitive and Movement Disorder Clinics by Drs. [name] and [name]. Potential participants will undergo a neurological and neuropsychological examination to characterize their medical and neurobehavioral status. Patients will have medical and motor presentation indicated for the community-based exercise program. Those patients with clinically-defined MCI, will be without evidence of vascular cognitive impairment, primary mood disorder, Lewy body disease, or comorbid medical condition that could contribute to cognitive symptoms (e.g. pulmonary, hematologic, metabolic, or vitamin deficiency).

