A.1.1.1. Clinical and neuropsychological examination. All potential participants will undergo baseline clinical and neuropsychological examination to determine eligibility, categorize MCI status, and provide quantification of neurocognitive functioning and neuropsychiatric symptomatology. The neuropsychological examination protocol will consist of memory measure (i.e., the Hopkins Verbal Learning Test – Revised [HVLT-R], consisting of Learning, Recall, and Recognition subcomponents). We will also administer three executive functioning measures (i.e., Trail Making Test – A & B57, Verbal Fluency [FAS], Stroop]), to facilitate exploratory analyses. To evaluate sleep disturbance symptomatology, PROMIS – Sleep Disturbance (SD) and Sleep-related Impairment (SRI) short forms will be administered.

A.1.1.2. PET. A single administration of approximately 370 MBq (10 mCi) Florbetapir 18F, then a 10- minute PET acquisition (2 × 5 minute frames) approximately 50 minutes later will be performed. Images will be reconstructed using an ordered subset estimation algorithm (4 iterations, 16 subsets, with a post-reconstruction Gaussian filter of 5 mm), and corrected for scatter and attenuation. Images will be co-registered to the high spatial resolution T1-weighted image as we have performed previously and a mean cortical:cerebellar SUVr will be calculated as the primary parameter of interest. For exploratory evaluation, we will also record SUVr in bi-temporal, bi-occipital, bi-frontal, and biparietal lobes.

A.1.1.3. MRI. The following imaging and angiography sequences will be completed. We will apply our previously reported 3T methods (16-channel neurovascular coil) with the below 50 min protocol:

Anatomical imaging. T1-weighted (MPRAGE; spatial resolution=1.0x1.0x1.0mm3; 3D turbo-gradient-echo; TR/TE=8.2/3.7ms), and T2-weighted (FLAIR; spatial resolution=0.9x1.1x3.0mm3; turbo-inversion-recovery; TR/TI/TE=11000/2800/120ms) imaging, and intracranial (spatial resolution = 0.5x0.8x1.4mm3; 3D gradient

echo; TR/TE=23/3.5ms) and extracranial (spatial resolution=0.9x0.9x3.0mm3 ; 2D gradient echo; TR/TE=18.6/3.2ms) time-of-flight (TOF) MR angiography (MRA).

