A.1.3. Statistical concerns. Statistical analyses will be overseen by statistician Co-I [name]. Descriptive statistics, including means, standard deviations, and ranges for continuous parameters, as well as percent and frequency for categorical parameters, will be presented. Tests for normality and homoscedasticity will be made. To test Hypothesis (1A), Pearson or Spearman (depending on normality findings) will be applied to evaluate the relationship between glymphatic flow, measured as the DTIALPS score, and the cortical:cerebellar SUVr, measured from PET. As an exploratory analysis to understand whether the relationship is spatially dependent, correlation testing will be repeated using the regional SUVr measures and corrected p-values reported. Power calculations are based on preliminary data in six MCI subjects in which an inverse correlation (Spearman's alpha =-0.49) was found between SUVr and DTI-ALPS score. With a sample size of 32, we should have 82% power to detect a correlation of -0.49 with two-sided p<0.05. To test Exploratory Hypothesis (1B), we will apply a Student's t-test or Wilcoxon rank-sum test (depending on normality findings), to evaluate whether mean glymphatic flow, measured as the DTI-ALPS score, is different between age- and sex-matched participants with vs. without MCI. Motivation is based on our preliminary data, where we have observed a large effect size (Cohen's d=2.3) in DTI-ALPS score between age- and sex-matched subjects with vs. without MCI.

A.1.4. Impact. Results will for the first time evaluate how the proposed human CNS lymphatic system and levels of beta-amyloid burden are altered in Parkinson's disease. If confirmed, results will motivate the use of evaluating human CNS lymphatic dysfunction with proposed methods for understanding betaamyloid clearance disorders.

A.2. Aims (2). Quantify the glymphatic functioning and beta-amyloid burden response to 12 weeks of a community-based exercise course developed specifically for PD patients.

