procedure will be applied to evaluate differences in SUVr pre vs. post exercise intervention and corrected pvalues will be reported. To gain additional information, a multiple linear regression will be performed using the change in glymphatic flow (DTI-ALPS score) as the dependent variable and degree of compliance and change in beta-amyloid burden as the independent variables. To test Exploratory Hypothesis (2C), we will perform these same comparisons separately for MCI and non-MCI subgroups. Aim 2 hypotheses are exploratory, given limited extant literature defining reliable effect sizes; however, one randomized study (n = 33) demonstrated a 30% divergence in mean plasma levels of a CSF beta-amyloid marker between exercise (-6%) and non-exercise participants (+24%) with MCI. Thus, with the proposed sample size of 32 (each with a measurement before and after intervention), we should have at least 80% power to detect a significant difference in mean DTI-ALPS score pre- vs. post-exercise with at least 80% power and two-sided Type I error=5%. We should also have sufficient power to include two independent variables in the regression model. *A.2.3. Impact.* Results will provide evidence of how CNS lymphatic and beta-amyloid properties adjust in response to regular vigorous exercise in a PD sample.

A.3. Aim (3). Evaluate the degree to which neuroimaging-based response to exercise mediates clinical improvement in neurocognitive functioning and neuropsychiatric symptomatology.

Hypothesis 3.A. Neurocognitive functioning will improve following completion of the exercise intervention. Exploratory Hypothesis (3.B.). Sleep disturbance symptoms will diminish following completion of the exercise intervention.

Exploratory Hypothesis (3.C.). The degree of change glymphatic function and cortical beta-amyloid uptake in response to exercise therapy will be correlated with the degree of improvements in neurocognitive functioning.

Exploratory Hypothesis (3.D.). The degree of change glymphatic function and cortical beta-amyloid uptake in response to exercise therapy will be correlated with the degree of improvements in sleep disturbance symptomatology.

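### The SAP and the protocol give different sample sizes, PET scans and exercise schedules, so the SAP's power statements and hypotheses belong to a design that the protocol does not describe

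*SAP*

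**What the plan says.** **Sample size.** SAP A.1.1 enrols "n=32; age range=55- 80 years), equally distributed and matched for age and sex between groups with (n=16) and without (n=16) mild cognitive impairment". Protocol 2.1 describes the same cohort as "n=50; age range=55-80 years), equally distributed and matched for age and sex between groups with (n=25) and without (n=25) mild" cognitive impairment. SAP A.1.3 states: "With a sample size of 32, we should have 82% power to detect a correlation of -0.49 with two-sided p<0.05". SAP A.2.2 bases its power claim on the same number, "with the proposed sample size of 32 (each with a measurement before and after intervention". SAP section B adds: "We have accounted for a possible 10% attrition/exclusion in our protocol".

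**PET.** SAP Hypothesis 1A expects glymphatic flow and lymphatic velocity to "inversely correlate with beta amyloid measured from 18F-florbetapir PET in older adults". SAP A.1.1.2 specifies "A single administration of approximately 370 MBq (10 mCi) Florbetapir 18F", followed by a 10-"minute PET acquisition (2 × 5 minute frames) approximately 50 minutes later will be performed". Protocol 2.1 and 2.2 (Imaging, PET/CT) specify C11PiB, 555 MBq, and a 70-minute dynamic acquisition. Both documents derive a mean cortical:cerebellar SUVr, and the protocol synopsis lists it as a primary endpoint.

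**Exercise.** SAP A.2.1.1 has 12 weekly classes of 90 minutes, and A.2.2 words the main Aim 2 hypotheses for weekly exercise. Protocol 2.2 (Exercise) has 60-minute classes, 20 class credits and attendance of about two classes a week. The synopsis timeline lists two a week.

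**The concern.** The SAP should analyse the trial that the protocol runs. Three defining features differ: how many people are enrolled, how a primary endpoint is acquired, and what the participants are exposed to. None of these is a slip of one digit.

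Three things are at stake. First, the planned n is undetermined, and the documents give no power statement for 50. Second, Hypothesis 1A names a tracer that the protocol does not use, so as written it cannot be tested on the protocol's scans. The protocol also does not say which part of its long dynamic scan forms the SUVr, so two analysts could compute the primary endpoint from different minutes of the same scan. Third, degree of compliance is a regression variable in SAP A.2.2, but full compliance could mean 12, 20 or 24 classes depending on the passage read.

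**Working it through.** **1. The SAP's own power figure (A.1.3).** Inputs: r = -0.49, n = 32, two-sided 5%. By Fisher's z,

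power = Φ(atanh(0.49) × √(n − 3) − 1.96), with atanh(0.49) = 0.536.

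At n = 32: 0.536 × √29 − 1.96 = 0.927, and Φ(0.927) = 82.3%. The stated 82% is reproduced.

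**2. The same formula at the other sizes.** A.1.3 allows Spearman's correlation if normality fails, so the last column uses the larger variance (1 + 0.49²/2)/(n − 3).

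| n analysed | Where it comes from | Fisher z | Spearman variance |
|---|---|---|---|
| 29 | 32 less 10% (28.8) | 78.0% | 73.3% |
| 32 | SAP | 82.3% | 77.9% |
| 45 | 50 less 10% | 93.5% | 90.7% |
| 50 | Protocol | 95.7% | 93.5% |

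**3. Does the 10% allowance link 32 and 50?** No. 32/0.9 = 35.6, so 36 enrolled would leave 32, while 50 × 0.9 = 45. Within the SAP, 32 is both the number enrolled (A.1.1) and the number with measurements before and after exercise (A.2.2), so no allowance is visible there.

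**4. Aim 2.** A.2.2 gives no standardised DTI-ALPS effect, so its 80% claim cannot be reproduced at any n. For illustration, the smallest standardised paired change (dz) detectable with 80% power by a two-sided 5% paired t-test (noncentral t, n − 1 degrees of freedom, noncentrality dz × √n) is:

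- whole cohort: 0.51 at 32, 0.43 at 45, 0.40 at 50;
- each MCI or non-MCI subgroup (Hypothesis 2C): 0.75 at 16, 0.58 at 25.

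**5. PET frames.** The protocol's frames number 4 + 8 + 9 + 2 + 10 = 33. They last 4×15 + 8×30 + 9×60 + 2×180 + 10×300 = 4,200 s = 70 minutes, so the protocol's total is consistent. The first 23 frames end at 1,200 s = 20 minutes, and frames 24 to 33 are ten 5-minute frames covering 20 to 70 minutes. If the scan starts at injection (an assumption), the SAP's window of two frames at about 50 minutes would fall on frames 30 and 31 (50 to 60 minutes). No passage applies that window to the C11PiB scan, and none gives another.

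**6. Exercise.**

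- SAP: 12 × 90 = 1,080 minutes, one class a week.
- Protocol credits: 20 × 60 = 1,200 minutes, 20/12 = 1.7 classes a week.
- Protocol synopsis, two a week for 12 weeks: 24 × 60 = 1,440 minutes.

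Credits against SAP classes: 20/12 = 1.67, or 67% more classes, but 1,200/1,080 = 1.11, or 11% more class time. Credits are an entitlement and the SAP's classes are a prescription, so the first ratio is not quite like for like.

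**The case against.** The best defence is that the differences matter less than they look.

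- **Much agrees.** Age range, matching, the MCI contrast, the MRI sequences, DTI-ALPS, SUVr as the PET measure, reconstruction settings, the 12-week period and the before-and-after design are common to both. This is true, and the conflict is limited to the three features above.
- **The tests do not change.** A.1.3 and A.2.2 name SUVr without a tracer or time window. This stands for the choice of test. It does not settle what number enters the test, or the wording of Hypothesis 1A.
- **The missing SUVr window is a protocol omission, not a contradiction.** Partly right: it would remain if the SAP were withdrawn. The SAP does not fill the gap, because its timing describes a different tracer's acquisition.
- **50 exceeds 32, so nobody is harmed.** Power does rise. But if 32 are enrolled and 10% are lost, it falls to 78.0%.
- **The -0.49 is fragile.** It comes from six MCI subjects, and its Fisher-z 95% interval is about -0.93 to +0.53 (0.536 ± 1.96/√3, back-transformed, with the sign reversed). The power figures above are therefore conditional on that value. The documents also do not say which tracer produced it.
- **Attendance is free.** The protocol excludes nobody for attendance and the SAP treats compliance as a scalar. That softens the exercise conflict but leaves the scale undefined.
- **One text may simply be older.** Version dates were not seen. They could show which is newer, but they would not make the texts agree.

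**Conclusion.** The concern holds, with high confidence. Sample size (32 against 50), PET (tracer, activity and acquisition) and exercise schedule (weekly 90-minute classes against 60-minute classes about twice a week) conflict in current text. The SAP's 82% is correct by Fisher's z for 32 analysed with no loss, but it is not the power of the protocol's design, which is 93.5% at 45 and 95.7% at 50. These figures assume a true correlation of -0.49.

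The PET conflict carries the most weight, because it concerns a primary endpoint whose time window is not stated for the protocol's scan. The n and class-schedule conflicts are mainly a matter of alignment, but they leave the power statements and the compliance scale without a settled basis. All three should be resolved before analysis. No view is taken on which tracer, activity or class schedule is right.

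**What to change.** 1. State one n in both documents. Restate the Aim 1 and Aim 2 power on the number evaluable after 10% loss (50 enrolled leaves 45; 32 evaluable needs 36 enrolled), and say which figure carries the allowance.
2. The investigators must reconcile the tracer, activity and acquisition passages, and the class-schedule passages, across the two documents.
3. Reword Hypothesis 1A and the Aim 2 hypotheses to match the result.
4. Before analysis, state which frames or minutes form the SUVr for the tracer actually used.
5. Give the unit and the maximum of the compliance variable.

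If the reconciliation only updates text, the cost is an amendment to the SAP, the protocol or both. If it changes what is actually done, the cost is larger and cannot be judged from the documents.

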Spin labeling for cervical LN perfusion. Spin labeling will be performed with an 11-ms hypersecant inversion (labeling) prepulse, followed by an inversion time range of 300 to 2400 ms in 300 ms increments, which will enable blood transit time and perfusion quantification. Other parameters: labeling=STAR; TE=11 ms; spatial resolution=2x2x2 mm3; averages=14.

A.1.2. Analysis and statistical plan.

A.1.2.1 Clinical and neuropsychological examination. MCI will be defined based on established clinical criterion of cognitive performance below 1.5 standard deviations compared to age-based normative expectations in the memory domain and/or the executive functioning domain, with a Clinical Dementia Rating (CDR) of 0 or 0.5, indicating cognitive dysfunction has not contributed to functional dependence for activities of daily living61, 62. The memory domain by determining the mean memory score across performance on the HVLT-R (i.e., Learning Trials 1- 3, Delayed Recall, Delayed Recognition). Similarly, an executive functioning domain will be determined by the mean score across the TMT (part B), Stroop, and Letter Fluency. Clinical analyses will be overseen by Drs. [name] and [name].

A.1.2.2. Image analysis. Analysis will be overseen by the PI and radiology Co-Is Drs. [name] and [name], who together have experience with all image types. Lymphatic spin labeling. Sequential images are acquired (A) without and (B) with magnetic labeling (adiabatic inversion of arterial water spins). Following labeling, blood water flows into LNs (C,D) and attenuates signal. The difference image is proportional to perfusion

(ml/100g/min), which can be quantified upon application of the flow modified Bloch equation (E: T2-weighted image of LNs; F: corresponding perfusion weighted signal). (G) The blood arrival (red) and lymph arrival (black) following labeling over six subjects and LNs (dimensions shown above). The blood signal peaks and decays first, with the magnitude indicating perfusion. The lymph signal peaks later, due to slower lymphatic flow; note that the lymphatic signal is detectable at such long delays due to the longer T1 of lymph (T1=3100 ms) relative to blood (T1=1650 ms).

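### The executive domain uses TMT part B without correcting for part A, so a gain in motor speed after exercise can count as executive improvement in Hypotheses 3A and 3C

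*SAP*

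**What the plan says.** SAP A.1.2.1 builds two cognitive domains. Memory is the average of the HVLT-R components. For the other, the "executive functioning domain will be determined by the mean score across the TMT (part B), Stroop, and Letter Fluency". The same section uses both domains to define MCI as "cognitive performance below 1.5 standard deviations compared to age-based normative expectations in the memory domain and/or the executive functioning domain". It does not say on what scale the components are averaged when the domain is used in Aim 3, and it does not say how Stroop is scored.

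SAP A.3.2 tests Hypothesis 3A with a paired t-test or signed-rank test to "determine if memory and executive functioning domain averages are improved after, relative to before, exercise intervention". For Hypothesis 3C it enters the mean memory and "mean executive functioning domain scores as independent variables" in two regressions, one on DTI-ALPS and one on SUVr. No motor measure is named as a covariate in either analysis.

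A.3.2 says the aim was powered on published effects. The within-subject one is "TMT-B-A time, np2's = 0.34; n = 19". The between-subject ones are "spatial working memory task, np2 = 0.17; MoCA global cognitive screen, np2 = 0.133; Treatment n = 24, Control n = 9".

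TMT parts A and B are both given at baseline (SAP A.1.1.1), and the same battery is repeated at follow-up (SAP A.3.1). The Protocol synopsis lists both parts among the secondary endpoints. Protocol 2.2 (Exercise) describes a class designed for people with the gait, balance and motor problems of Parkinson's disease. SAP A.1.1 describes one cohort measured before and after exercise, with no control arm.

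**The concern.** Time on part B is the sum of hand and search speed and the cost of switching between sequences. Part A carries most of the first and little of the second, which is why B-A is used as a purer executive score. A patient who only moves faster at follow-up improves on part B with no executive change. With no control arm and no adjustment for part A or UPDRS-III, nothing in the planned analysis would reveal this.

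Two results are exposed. Hypothesis 3A is the one Aim 3 hypothesis without an exploratory label, and its executive half could be positive for motor reasons. In 3C, an association between imaging and the executive score could be an association with motor speed under a cognitive name. That bears on the Protocol's objective about imaging response mediating clinical improvement.

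The effect size is a separate mismatch: it comes from a score that removes speed, and the test is run on a composite that keeps it.

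**Working it through.** **Plan's own figure.** Aim 3 states no power and no sample size, so there is nothing to reproduce. A.3.2 carries over the Aim 1 considerations (n=32, two-sided 5%). The Aim 1 figure of 82% for r=-0.49 does reproduce: atanh(0.49) × √29 = 2.89, and Φ(2.89 - 1.96) = 82.3%. The Protocol (2.1) gives n=50, so both sizes are used below.

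**1. What the cited effect implies.** Take partial eta squared 0.34 with n=19 as a one-group, two-time contrast.
- F = 0.34/0.66 × 18 = 9.27, so t = 3.05 and dz = √(9.27/19) = 0.70.
- Paired-t power for dz = 0.70 is 96.9% at n=32 and 99.8% at n=50, but only for a B-A endpoint.
- The composite needs dz of about 0.51 at n=32, or 0.41 at n=50, for 80% power. The documents give no effect size or SD for it.

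**2. Leakage if only part B gains speed.** Assumptions, none of them from the documents: a purely motor gain of 10 s, no executive change, a normative SD for part B of 30-40 s, an SD of domain change of 0.4-0.5 (in normative SD units), and no shift in Stroop or Letter Fluency.
- Shift in the domain mean = (10 / normative SD) / 3, which is 0.083 (SD 40) to 0.111 (SD 30).
- Standardised change d = shift / SD of change, which is 0.083/0.5 = 0.167 to 0.111/0.4 = 0.278.
- Two-sided 5% paired t-test, noncentral t:

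| Setting | n=32 | n=50 |
|---|---|---|
| 10 s gain, SD of change 0.4-0.5 | 15-33% | 21-49% |
| 10 s gain, SD of change 0.6-0.8 | 9-17% | 11-25% |
| 5 s gain, SD of change 0.4-0.5 | 7-12% | 9-16% |

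The nominal rate is 5%. With B-A, a speed gain that shortens A and B by the same number of seconds contributes zero from the TMT.

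**3. Cross-check on another scale.** Standardise each component by the SD of its own change, weight the three equally, and let changes correlate at ρ. If part B alone shifts by d, the composite has dz = d/√(3 + 6ρ). For ρ from 0.5 to 0, the chance of a significant result in the direction of improvement (nominal 2.5%) is:

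| Part B shift | n=32 | n=50 |
|---|---|---|
| 0.3 SD | 10-16% | 13-22% |
| 0.5 SD | 20-35% | 29-52% |
| 0.7 SD | 35-60% | 51-80% |

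Both models agree on direction. Neither can say which row applies to this trial.

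**The case against.** The best reply is that the leakage is limited and its premise is assumed. Part B is one of three components, so any speed gain is diluted by a factor of three. The class targets motor symptoms, but the documents do not show that it quickens the hand. With a 5 s gain the false-claim rate at n=32 is 7-12%, not far above 5%. SAP A.1.1.1 also presents the executive tests as serving exploratory analyses. All of this stands, and it is why the size is given as a range and the remedy is modest.

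A reader might go further in several directions that the documents do not support:
- **That part B enters as raw seconds.** The SAP does not say so, and A.1.2.1 judges the domain against age norms. The point does not depend on it, because age norming leaves a within-person speed gain in place.
- **That UPDRS-III is predicted to improve.** It is a listed endpoint, but no hypothesis about it appears in the SAP.
- **That two of the three tests leak.** This would need Stroop to be scored on time and to shift as much as part B. Its scoring is not stated.
- **That 3A as a whole is uninterpretable.** The memory half rests on HVLT-R learning, recall and recognition, which the timed-drawing argument does not touch.
- **That MCI grouping and Hypothesis 1B need repair too.** Adding TMT-A as a covariate in 1B would reclassify nobody, and rescoring MCI would disturb the equal, matched groups.

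It is also fair to say that none of the three cited effects matches the composite. Putting B-A into one component does not make 0.34 apply to the average of three.

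**Conclusion.** The point holds for the executive domain in Hypotheses 3A and 3C. The plan scores TMT part B uncorrected for part A and cites a within-subject effect for B-A. It collects part A at both visits without using it, and it has neither a control arm nor a motor covariate to separate speed from executive change. A positive executive result in 3A would therefore be open to a motor explanation.

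The size is not determined by the documents. With part B alone affected, a 10 s motor gain, a normative SD of 30-40 s and an SD of domain change of 0.4-0.5, a significant result with no executive change has a probability of about 15-33% at n=32 and 21-49% at n=50. Smaller gains or larger SDs bring it down towards 5%. The memory domain, MCI classification and Hypothesis 1B lie outside the point. This is an inexpensive improvement in how a secondary result can be read; it does not undermine the primary endpoints.

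**What to change.** In SAP A.1.2.1 and A.3.2, for the executive domain used in 3A and 3C only:
- Replace part B with TMT B-A, or with part B adjusted for part A. If part B is kept, report the domain both ways and claim executive improvement only if it holds with the part-A-corrected score.
- Report TMT-A and part B separately as speed measures.
- State how Stroop is scored. If it is timed, use the interference contrast.
- State the scale and direction of each component in the average.
- State that the cited 0.34 is for TMT B-A and does not apply to the three-test composite.

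Leave MCI classification and Hypothesis 1B as they are.

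The cost is SAP wording and rescoring of data already due at both visits, with no new test or visit. The drawback is that a difference score is somewhat noisier than part B alone, so the executive test may lose some power.
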